8.1.2. Secondary Efficacy Assessments

MMPS-P and lower facial width assessments will be completed at screening, baseline, and at each scheduled visit thereafter until study exit. The PSAC will be completed at all scheduled postbaseline visits. Participants will be trained on how to properly complete the MMPS-P and PSAC assessments using images, at the Screening Visit (and at other visits if needed).

Masseter Muscle Prominence Scale – Participant (MMPS-P)

MMP assessed by the participant is a secondary efficacy assessment developed by the sponsor through concept elicitation and cognitive debriefing. Participants will be asked to assess the severity of their masseter prominence using a single question composed of 5 grades (1 = not at all pronounced, 2 = mildly pronounced, 3 = moderately pronounced, 4 = pronounced, 5 = very pronounced;

Participant Self-Assessment of Change (PSAC)

The PSAC is a commonly used assessment of change scale that has been adapted for use with MMP by the sponsor using concept elicitation and cognitive debriefing. Participants will be asked to assess change of their lower face shape using 2D images collected before study intervention (ie, baseline, or screening if the baseline image is not of acceptable quality) and after study intervention (ie, the current study visit)

The participant will answer the questions on the accompanying assessments via electronic tablet that will be provided to the study participant at the study site.

Lower Facial Width

The lower facial width (mm) will be calculated from 2D projections of 3D images.

8.1.3. Other Efficacy Assessments

8.2. Safety Assessments

Planned timepoints for all safety assessments are provided in the SoA (see Section 1.3).

8.2.1. Vital Signs

CONFIDENTIAL

Vital signs will be assessed as follows:

- Pulse rate, respiratory rate, and blood pressure will be assessed.
- Blood pressure and pulse measurements will be assessed with participants in a sitting
 position after sitting for at least 5 minutes; use of either a manual or automated device is
 acceptable. Manual techniques will be used only by trained personnel; whenever possible, the
 same person should perform all manual assessments as much as possible.
- Height and weight will also be measured and recorded, and BMI calculated at the screening visit.

8.2.2. Pregnancy Testing

Pregnancy testing will be conducted at the screening, baseline retreatment, and study exit visits. Urine pregnancy tests will be used unless the study site requires the use of serum testing, in which case serum testing will be used. Females of childbearing potential must have a negative test result before receiving study treatment/retreatment. This test may also be performed at any other visit, at the investigator's discretion. At each visit, the investigator should discuss contraceptive use compliance with females of childbearing potential.

8.2.3. Screening for TMJD

Screening for signs/symptoms of possible TMJD will be conducted by the investigator at the screening visit, as described in the Study Manual. Depending on the findings, the investigator may decide to exclude the participant from the study, or may refer the participant to a dentist for further TMJD screening, to be completed prior to Day 1. The participant may complete the rest of the planned activities and procedures for the screening visit, with the dentist examination occurring at a later time. If, based on findings from a dental examination, the dentist diagnoses the participant with TMJD, the participant will be considered a screen failure.

8.3. Adverse Events and Serious Adverse Events

The definitions of an AE or SAE can be found in Appendix 2.

AEs will be reported by the participant (or, when appropriate, by a caregiver, surrogate, or the participant's legally authorized representative).

The investigator and any qualified designees are responsible for detecting, documenting, and recording events that meet the definition of an AE or SAE and remain responsible for following up AEs that are serious, considered related to the study intervention or study procedures, or that caused the participant to discontinue the study intervention (ie, repeat treatment) or study (see Section 7).

8.3.1. Time Period and Frequency for Collecting Adverse Event and Serious Adverse Event Information

All SAEs from the signing of the ICF will be collected at the timepoints specified in the SoA (Section 1.3), and as observed or reported spontaneously by study participants.

All AEs from the signing of the ICF will be collected at the timepoints specified in the SoA (Section 1.3), and as observed or reported spontaneously by study participants.

Medical occurrences that begin before the start of study intervention, but after obtaining informed consent, will be recorded in the AE section of the eCRF and will be considered pretreatment AEs.

All SAEs will be recorded and reported to the sponsor or designee within 24 hours, as indicated in Appendix 2. The investigator will submit any updated SAE data to the sponsor within 24 hours of it being available.

Investigators are not obligated to actively seek AE or SAE information after conclusion of the study participation. However, if the investigator learns of any SAE, including a death, at any time after a participant has been discharged from the study, and he/she considers the event to be reasonably related to the study intervention or study participation, the investigator must promptly notify the sponsor.

The methods of recording, evaluating, and assessing causality of AEs and SAEs and the procedures for completing and transmitting SAE reports are provided in Appendix 2.

8.3.2. Method of Detecting Adverse Events and Serious Adverse Events

Care will be taken not to introduce bias when detecting AEs and/or SAEs. Open-ended and non-leading verbal questioning of the participant is the preferred method to inquire about AE occurrences.

8.3.3. Follow-up of Adverse Events and Serious Adverse Events

After the initial AE/SAE report, the investigator is required to proactively follow each participant at subsequent visits/contacts. All SAEs and any AESI as defined in Appendix 2 will be followed

CONFIDENTIAL Protocol 1789-301-008

BOTOX

until resolution, stabilization, the event is otherwise explained, or the participant is lost to followup (as defined in Section 7.3).

The investigator is obligated to perform or arrange for the conduct of supplemental measurements and/or evaluations as medically indicated or as requested by the sponsor to elucidate the nature and/or causality of the AE or SAE as fully as possible. This may include additional laboratory tests or investigations, histopathological examinations, or consultation with other health care professionals. If a participant dies during participation in the study, the investigator will provide the sponsor with a copy of any postmortem findings including histopathology.

New or updated information will be recorded in the originally completed eCRF.

The investigator will submit any updated SAE data to the sponsor within 24 hours of receipt of the information.

8.3.4. Regulatory Reporting Requirements for Serious Adverse Events

- Prompt notification by the investigator to the sponsor of an SAE is essential so that legal
 obligations and ethical responsibilities towards the safety of participants and the safety of a
 study intervention under clinical investigation are met.
- The sponsor has a legal responsibility to notify both the local regulatory authority and other
 regulatory agencies about the safety of a study intervention under clinical investigation. The
 sponsor will comply with country-specific regulatory requirements relating to safety
 reporting to the regulatory authority, IRBs/ IECs, and investigators.
- Investigator safety reports must be prepared for SUSARs according to local regulatory requirements and sponsor policy and forwarded to investigators as necessary.
- An investigator who receives an investigator safety report describing an SAE or other specific safety information (eg, summary or listing of SAEs) from the sponsor will review and then file it along with the investigator's brochure and will notify the IRB/IEC, if appropriate according to local requirements.

8.3.5. Pregnancy

- If a pregnancy is confirmed after the participant has received the study intervention, the
 participant may choose to exit the study after appropriate safety follow-up or to remain in the
 study for all safety and efficacy follow-up assessments through the end-of-study visit.
- Details of all pregnancies in female participants will be collected from the signing of the ICF and through the duration of the pregnancy.
- If a pregnancy is reported, the investigator should inform the sponsor within 24 hours of learning of the pregnancy and should follow the procedures outlined in Appendix 6.

Abnormal pregnancy outcomes (eg, spontaneous abortion, fetal death, stillbirth, congenital
anomalies, ectopic pregnancy) or genetic abnormalities (whether leading to an elective
abortion or not) are considered SAEs.

8.3.6. Adverse Events of Special Interest

AESIs will be recorded as indicated in Appendix 2.

8.3.7. Medication Errors

Medication error refers to any unintended error in the dosing and/or administration of the study intervention as per instructions in the protocol, for example:

- Wrong study drug
- Wrong dose (including dosing regimen, concentration, amount)
- Wrong participant (ie, not administered to the intended participant)

8.4. Treatment of Overdose

The LD50 for BOTOX in humans is estimated from primate studies to be approximately 3000 U. This makes accidental injection of a lethal dose highly unlikely, but significant AEs may still occur at doses below the LD50 (Herrero 1967, Scott 1989).

Excessive doses may produce local or distant, generalized, and profound neuromuscular paralysis. Should accidental injection or oral ingestion occur, or overdose be suspected, the participant should be medically monitored for up to several weeks for progressive signs or symptoms of systemic muscular weakness that could be local or distant from the site of injection, and which may include ptosis, diplopia, dysphagia, dysarthria, generalized weakness, or respiratory failure. Please refer to the general Section 6.5 of the BOTOX MMP investigator's brochure for further details.

In the event of an overdose, the investigator should:

- Contact the medical safety physician immediately.
- Closely monitor the participant for AEs and SAEs.
- Document the quantity of the excess dose as well as the duration of the overdose in the eCRF as well as other details that led to the overdose.

8.5. Pharmacokinetics

Pharmacokinetic parameters are not evaluated in this study.

8.6. Pharmacodynamics

Pharmacodynamic parameters are not evaluated in this study.

8.7. Genetics

Genetics are not evaluated in this study.

8.8. Biomarkers and Other Assessments

Biomarkers are not evaluated in this study.

8.9. Health Economics

Health economics parameters are not evaluated in this study.

9. Statistical Considerations

9.1. Statistical Hypotheses

The following set of hypotheses will be used to compare the BOTOX 72 U group with placebo:

- Null hypothesis: BOTOX and placebo are equally effective in reducing MMP as measured by the proportion of responders achieving ≥ 2-grade improvement from baseline at Day 90 using the MMPS.
- Alternative hypothesis: BOTOX and placebo are not equally effective in reducing MMP as measured by the proportion of responders achieving ≥ 2-grade improvement from baseline at Day 90 using the MMPS.

9.2. Sample Size Determination

approximately 360 participants (270 BOTOX and 90 placebo) will provide > 90% power

9.3. Populations for Analyses

The analysis populations will consist of participants as defined in below:

- The mITT population includes all randomized participants with ≥ 1 postbaseline MMPS
 assessment. Participants will be summarized according to the randomized study
 intervention.
- The safety population includes all treated participants who receive ≥ 1 administration of study intervention. Participants will be summarized according to the study intervention they received.

9.4. Statistical Analyses

The SAP will be developed and finalized before database lock and unblinding and will describe the participant populations to be included in the analyses, and procedures for accounting for missing, unused, and spurious data. This section is a summary of the planned statistical analyses of the primary and secondary endpoints. Planned analyses of other efficacy endpoints and other collected clinical and safety data from this study will be fully documented in the study SAP.

9.4.1. Efficacy Analyses

The efficacy analyses will be based on the mITT population. Baseline for efficacy is defined as the last nonmissing efficacy assessment before the first dose of study intervention. All statistical tests will be 2-sided hypothesis tests performed at the 5% level of significance for main effects.

The overall familywise error rate will be controlled at $\alpha = 0.05$ for the set of primary and secondary endpoint comparisons between BOTOX 72 U vs placebo. The overall serial gatekeeping MCP is defined in Table 9-1.

9.4.1.1. Analysis Endpoints

The primary and secondary efficacy endpoints are listed below, and analyses will be defined in the following sections. All analyses for other efficacy endpoints listed below will be defined in the SAP.

[figure not shown]
Primary efficacy endpoint:

 Proportion of responders who achieve ≥ 2-grade improvement from baseline at Day 90, per investigator assessments of MMP using the MMPS

[figure not shown]

Secondary efficacy endpoints:

- Proportion of responders who achieve MMPS Grade ≤ 3 at Day 90, according to investigator
- Proportion of responders who achieve MMPS-P Grade ≤ 3 at Day 90, according to participant
- Proportion of responders who achieve ≥ 2-grade improvement from baseline at Day 90 using the MMPS-P
- Proportion of responders who achieve PSAC Grade ≥ 1 (at least minimally improved from baseline) at Day 90
- Change from baseline in lower facial width (mm) at Day 90

Other endpoints:

9.4.1.2. Primary Analyses

The primary efficacy endpoint will be the proportion of responders who achieve ≥ 2-grade improvement from baseline at Day 90, per investigator assessments of MMP using the MMPS and will be analyzed using CMH model stratified by baseline MMPS Grade (4 or 5). Missing MMPS values in Period 1 will be imputed using multiple imputation methods. A sensitivity analysis will be based on observed data.

BOTOX

[figure not shown]
9.4.1.3. Secondary Analyses

MMPS responders will be defined as participants who achieve MMPS Grade ≤ 3 .

MMPS-P responders will be defined as:

- Participants who achieve MMPS-P Grade ≤ 3
- Participants who achieve ≥ 2-grade MMPS-P improvement from baseline

The proportion of MMPS and MMPS-P responders as defined above and PSAC Grade ≥ 1 responders will be analyzed using CMH model stratified by baseline MMPS Grade (4 or 5).

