5.1. Inclusion Criteria

Participants are eligible to be included in the study only if all of the following criteria apply:

1.	Age
1.01	Participant must be at least 18 years of age (or older if legal age of adulthood is > 18 as per local regulations), at the time of signing the informed consent
2.	Type of Participant and Masseter Characteristics
2.01	Participant must be healthy as assessed by the investigator.
2.02	Participant has a marked (Grade 4) or very marked (Grade 5) bilateral MMP (identical grades for left and right masseter), as determined at the Day 1 visit by the investigator using the MMPS
2.03	Participant has a pronounced (Grade 4) or very pronounced (Grade 5) MMP, as determined at the Day 1 visit by the participant using the MMPS-P
3.	Body Mass Index
3.01	BMI \leq 30 kg/m ² using the calculation: BMI = weight (kg)/[height (m)] ²
4.	Sex
4.01	Male or female
5.	Contraceptives
5.01	A female participant must be willing to minimize the risk of inducing pregnancy for the duration of the clinical study and follow-up periods.

BOTOX

5.02	A female participant is eligible to participate if she is not pregnant (has a negative pregnancy result prior to randomization; see Appendix 6), not breastfeeding, and at least one of the following conditions applies: a. Not a WOCBP as defined in Appendix 6 OR b. A WOCBP who agrees to follow the contraceptive guidance in Appendix 6 during the treatment and follow-up period
6.	Informed Consent
6.01	Capable of giving signed informed consent as described in Appendix 1, which includes compliance with the requirements and restrictions listed in the ICF and in this protocol.
6.02	Written informed consent from the participant has been obtained prior to any study-related procedures.
6.03	Written documentation has been obtained in accordance with the relevant country and local privacy requirements, where applicable.
7.	Other
7.01	Able, as assessed by the investigator, and willing to follow study instructions and likely to complete all required study visits.

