6.3. Measures to Minimize Bias: Randomization and Blinding

At the Screening Visit, after the participant signs the ICF, the site will log on to the IWRS to obtain a participant number. On Day 1, the IWRS will be used to manage the randomization and assignment of participants into one of the 2 study intervention groups based on a randomization schedule prepared the sponsor's Biostatistics department. The randomization will occur after all baseline procedures have been completed and the investigator has verified that the participant has met all inclusion and exclusion criteria. Randomization will be stratified at each investigator site by the participant's baseline (Day 1) MMPS Grade (4 or 5), as assessed by the investigator.

For the double-blind Period 1, all study interventions will be provided in identical vials and cartons to maintain blinding. In addition, the injection volume and study intervention administration will be identical for both groups.

For open-label Period 2, all study intervention will be provided in cartons, each containing one open-label vial.

Study intervention will be labeled with kit numbers. The IWRS will provide the site with the specific kit number for each randomized participant at the time of randomization (Day 1). The IWRS will also issue the specific kit number for each participant who qualifies for retreatment. Sites will dispense study intervention according to the IWRS instructions. Sites will receive the IWRS confirmation notifications for each transaction and will maintain these with the study source documents.

At each study site, a designated staff member will serve as the IDR for the double-blind Period 1. This person will be responsible only for blinded study intervention preparation during Period 1. This person will be a staff member with no study responsibilities that require interaction with participants and with participant efficacy or safety data. For Period 2, site personnel other than the IDR may be assigned to prepare open-label study interventions (BOTOX).

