#### 9.1 PRIMARY EFFICACY ENDPOINT

The primary efficacy assessment is masseter muscle prominence assessed by the investigator using the MMPS (1 = minimal, 2 = mild, 3 = moderate, 4 = marked, 5 = very marked).

The primary efficacy endpoint is the achievement of  $\geq$  2-grade improvement from baseline at Day 90 using the MMPS.

The following set of hypotheses will be used to compare the BOTOX 72 U group with placebo:

- Null hypothesis: BOTOX and placebo are equally effective in reducing MMP as measured by the proportion of participants achieving ≥ 2-grade improvement from baseline at Day 90 using the MMPS.
- Alternative hypothesis: BOTOX and placebo are not equally effective in reducing MMP as measured by the proportion of participants achieving ≥ 2-grade improvement from baseline at Day 90 using the MMPS.

The proportion of participants who achieve  $\geq$  2-grade improvement from baseline, per investigator assessments of MMP using the MMPS, will be analyzed using Cochran-Mantel-Haenszel (CMH) model stratified by baseline MMPS Grade (4 or 5) at each visit. A 2-sided p-value  $\leq$  0.05 will be claimed as statistically significant. The Breslow-Day homogeneity of the odds-ratio test will be performed to test the interaction of treatment by baseline MMPS Grade. A

two-sided p-value  $\leq$  0.1 will be claimed as statistically significant. Responder rate 2-sided 95% CIs within each treatment group will be based on normal approximation to the binomial.

Sensitivity analyses will be performed for the primary efficacy variable based on observed data.

The attributes of the estimands corresponding to the primary efficacy endpoint are summarized in Table 2.

Table 2. Summary of the Estimand Attributes of the Primary Efficacy Endpoint

	Attributes of the Estimand							
Estimand Label	Treatment	Endpoint	Population	Handling of Intercurrent Events	Statistical Summary			
Hypothetical estimand for primary endpoint	BOTOX 72 U vs placebo	Achievement of ≥ 2-grade improvement from baseline based on MMPS at Day 90	mITT (all randomized participants with at least one postbaseline MMPS assessment)	Participants who discontinue prior to Day 90 assessments or who do not have Day 90 MMPS assessments will be included in the analysis as a hypothetical scenario in which they had not missed the MMPS assessments	Difference in response proportions between treatments after MI using CMH test stratified by baseline MMPS			

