## 9.2 SECONDARY EFFICACY ENDPOINTS

The secondary efficacy endpoints are:

- Achievement of MMPS Grade ≤ 3 at Day 90, according to investigator
- Achievement of MMPS-P Grade ≤ 3 at Day 90, according to participant
- Achievement of ≥ 2-grade improvement from baseline at Day 90 using the MMPS-P
- Achievement of PSAC Grade ≥ 1 (at least minimally improved from baseline) at Day 90
- Change from baseline in lower facial width (mm) at Day 90

Duration of effect for BOTOX-treated MMPS responders

The proportion of participants who achieve MMPS Grade  $\leq$  3, the proportion of participants who achieve MMPS-P Grade  $\leq$  3, the proportion of participants who achieve  $\geq$  2-grade improvement from baseline using the MMPS-P, and the proportion of participants who achieve PSAC Grade  $\geq$  1 will be analyzed in the same manner as that used to analyze the primary endpoint. Missing MMPS, MMPS-P, and PSAC values in Period 1 will be imputed using the same MI method as for primary endpoint.

Table 3. Summary of the Estimand Attributes of the Secondary Efficacy Endpoints

	Attributes of the Estimand								
Estimand Label	Treat- ment	Endpoint	Population	Handling of Intercurrent Events	Statistical Summary				
Hypothetical estimand for binary secondary endpoints	BOTOX 72 U vs placebo	Achievement of the following at Day 90:  • MMPS Grade ≤ 3  • MMPS-P Grade ≤ 3  • MMPS-P ≥ 2-grade improvement from baseline  • PSAC Grade ≥ 1	mITT (all randomized participants with at least one postbaseline MMPS assessment)	Participants who discontinue prior to Day 90 assessments or who do not have specified Day 90 secondary efficacy assessments will be included in the analysis as a hypothetical scenario in which they had not missed the assessments	Difference in response proportions between treatments after MI using CMH test stratified by baseline MMPS				
Hypothetical estimand for continuous secondary endpoints	BOTOX 72 U vs placebo	Change from baseline in lower facial width (mm) at Day 90	mITT (all randomized participants with at least one postbaseline MMPS assessment)	Participants who discontinue prior to Day 90 assessments or who do not have Day 90 lower facial width will be included in the analysis as a hypothetical scenario in which they had not missed the lower facial width assessments	Difference between treatments in LS Mean and SE after MI using ANCOVA				

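### MMPS-P Grade ≤ 3 is tested in strata of the investigator's baseline grade only, although the participant's own baseline grade decides whether 1 or 2 grades of improvement are needed

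*Protocol*

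**What the plan says.** Protocol 9.4.1.3 covers the binary secondary endpoints together: "MMPS-P responders as defined above and PSAC Grade ≥ 1 responders will be analyzed using CMH model stratified by baseline MMPS Grade" (4 or 5). SAP 9.2 analyses them in the same way as the primary endpoint, and SAP Table 3 gives their summary measure as "Difference in response proportions between treatments after MI using CMH test stratified by baseline MMPS". Baseline MMPS is the investigator's rating. It is also the randomisation stratum (Protocol 6.3, SAP 17.4).

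The participant's own grade is fixed at entry. Inclusion criterion 2.03 requires MMPS-P Grade 4 or 5, "as determined at the Day 1 visit by the participant using the MMPS-P". It is known before allocation: "The randomization will occur after all baseline procedures have been completed and the investigator has verified" eligibility (Protocol 6.3).

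In the visible text, baseline MMPS-P has three uses: eligibility, the reference for the ≥ 2-grade MMPS-P endpoint, and a descriptive summary in SAP 8.1. It is never an analysis stratum.

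**The concern.** The threshold is fixed at Grade 3, so the distance to response depends on the participant's starting grade: 1 grade from MMPS-P 4, 2 grades from MMPS-P 5. Baseline MMPS-P is therefore likely to be prognostic for this endpoint.

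The investigator's counterpart, MMPS Grade ≤ 3, is stratified by the grade that sets its own distance. The participant's endpoint is stratified by another person's grade, which carries that information only as far as the two raters agree.

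Two things are at stake for one secondary endpoint in the familywise-controlled gatekeeping procedure: some power, and adjustment for a chance imbalance in a value already collected. If an imbalance is noticed only after unblinding, any adjustment for it is post hoc.

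The ≥ 2-grade MMPS-P endpoint does not share the problem, because its required distance is 2 grades from either baseline.

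**Working it through.** **Inputs from the documents.** Two-sided 5% tests (Protocol 9.4.1); 270 BOTOX and 90 placebo (Protocol 9.2); 3:1 allocation stratified by baseline MMPS (Protocol 6.3); 15% dropout and 306 completers (Protocol 4.1).

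**The plan's own figure.** 306/(1 − 0.15) = 360, and 360 × 3/4 = 270, leaving 90. Both match. The stated power above 90% cannot be reproduced because the response rates behind it are not visible.

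**Assumed inputs.** 35% investigator Grade 5; agreement between the two baseline ratings of 50%, 70% or 90%; response rates as listed below; no missing data.

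**Hand check of one setting.** Take 50% agreement, so half of each MMPS stratum is MMPS-P 5. Response at MMPS-P 4 / 5 is 40% / 10% on placebo and 58% / 25% on BOTOX.

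- Marginal rates: placebo (0.40 + 0.10)/2 = 0.25; BOTOX (0.58 + 0.25)/2 = 0.415; difference 0.165.
- Variance of the difference, MMPS strata only: 0.25 × 0.75/90 + 0.415 × 0.585/270 = 0.00298; SE 0.0546.
- Variance with MMPS-P strata added: mean within-grade variance is (0.24 + 0.09)/2 = 0.165 on placebo and (0.2436 + 0.1875)/2 = 0.2156 on BOTOX, so 0.165/90 + 0.2156/270 = 0.00263; SE 0.0513.
- Reduction: 1 − 0.00263/0.00298 = 12%.
- Power is Φ[(difference − 1.96 × SE0)/SE], where SE0 is the SE under the null from pooled rates.
  - MMPS strata: pooled rate 0.25 × 0.25 + 0.75 × 0.415 = 0.374, SE0 = √(0.374 × 0.626 × (1/90 + 1/270)) = 0.0589. Power = Φ[(0.165 − 0.1154)/0.0546] = 82%.
  - Four strata: pooled rates 0.535 and 0.2125, mean variance 0.208, SE0 = √(0.208 × (1/90 + 1/270)) = 0.0555. Power = Φ[(0.165 − 0.1088)/0.0513] = 86%.

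**Simulation.** 8,000 trials per setting, blocks of 4 at 3:1 within baseline MMPS, CMH with 2 strata (MMPS) against 4 (MMPS x MMPS-P):

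| Placebo gap between baseline grades | Placebo 4 / 5 | BOTOX 4 / 5 | Power at 50% agreement | 70% | 90% |
|---|---|---|---|---|---|
| 40 points | 50% / 10% | 68% / 25% | 80→88% | 81→88% | 85→87% |
| 30 points | 40% / 10% | 58% / 25% | 82→87% | 83→86% | 84→86% |
| 17 points | 25% / 8% | 42% / 18% | 73→75% | 76→78% | 77→78% |
| 10 points | 35% / 25% | 52% / 40% | 77→78% | 77→78% | 78→78% |
| Large effect | 30% / 8% | 75% / 45% | 100% either way | 100% either way | 100% either way |

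The variance of the difference falls by 6–18%, 4–12%, 1–5% and about 0–1% in the first four rows. Changing the investigator Grade 5 share to 20% or 50% in the 30-point row at 50% agreement gives 83→87% or 82→86%.

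**Second simulation with other inputs.** Placebo 35% / 10%, BOTOX 52% / 25%; 30% or 50% of participants at MMPS-P 5. Power is 80.7–84.2% with MMPS strata and 82.5–84.5% with both grades. In an extreme case (placebo 50% / 5%, BOTOX 70% / 20%, 50% agreement) it is 85.3% against 93.6%. Mean treatment differences agree to within 0.001 across stratifications, so there is no systematic bias.

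**Type I error.** 4.5–5.3% across both simulations, under every stratification.

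**Chance imbalance.** With agreement *a*, the SD of the between-arm difference in MMPS-P 5 share within MMPS strata is √[a(1 − a)(1/270 + 1/90)]: 6.1 points at a = 0.5 and 3.7 points at a = 0.9. At a 30-point gap, 1 SD moves the estimate by 0.30 × 6.1 = 1.8 points or 0.30 × 3.7 = 1.1 points, which is 0.33 or 0.20 of its SE.

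**The ≥ 2-grade MMPS-P endpoint.** Power is 80–83% under either set of strata, a change of at most 0.2 point.

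**The case against.** The strongest reply is that nothing is wrong. The test is valid, its stratum is the randomisation stratum, protocol and SAP agree, and one method serves the primary and all binary secondary endpoints. On that view this is an efficiency preference. All of those facts stand, but stratifying by MMPS x MMPS-P keeps the randomisation stratum and only refines it.

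A second reply is that the size is built on assumptions. Most settings in the table have power between 73% and 85%, where a small variance gain moves power most. With the BOTOX rates raised until two-stratum power is about 94–97%, the gain is about 0.4 to 3.4 points (for example 94.3→96.1% at a 30-point gap and 50% agreement). The 8-point upper end needs a gap of 40 points or more and agreement of 70% or less, and 50% agreement makes the two ratings independent. This stands and is why the gain is given as a range that starts at zero.

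Third, the subgroup section, the gatekeeping table and the imputation details are not visible, so baseline MMPS-P may be used there and the endpoint's place in the testing order is unknown. That is true, and no effect on later tests is claimed. It does not alter the CMH stratum, which both documents name. The calculations also ignore missing data, whereas the planned test follows multiple imputation.

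Finally, the change would create sparse cells and give one endpoint different strata from the primary. This is a real but small cost.

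**Conclusion.** The point holds. MMPS-P Grade ≤ 3 is tested without adjustment for the baseline grade that, by definition, sets how far a participant must move. It is a matter of precision and chance imbalance on one secondary endpoint, not of validity or bias. The likely gain is about 0 to 8 percentage points of power: near zero with a weak baseline gradient or a large treatment effect, and largest with a steep gradient and poor rater agreement. These figures rest on assumed response rates, grade mix and agreement, since the documents give none, and on complete data. The change is worth making because it is cheap, but it is a modest improvement.

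**What to change.** Specify in SAP 9.2 and Table 3 that the CMH test for MMPS-P Grade ≤ 3 is stratified by baseline MMPS x baseline MMPS-P, and record this as a change from Protocol 9.4.1.3. Do it before unblinding; Protocol 9.4 allows for that: "The SAP will be developed and finalized before database lock and unblinding". Using the same strata for the ≥ 2-grade MMPS-P endpoint is optional, for consistency only.

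Keep the interaction test as SAP 9.1 has it: "The Breslow-Day homogeneity of the odds-ratio test will be performed to test the interaction of treatment by baseline MMPS Grade". Over four strata it would be unreliable, because the discordant cells can be small. With 90 placebo participants and 35% at investigator Grade 5, the expected placebo count at MMPS 5 / MMPS-P 4 is 90 × 0.35 × (1 − agreement): about 3, 6, 9 and 16 at 90%, 80%, 70% and 50% agreement. At MMPS 4 / MMPS-P 5 it is 90 × 0.65 × (1 − agreement): about 6, 12, 18 and 29. CMH tolerates such cells, and type I error held at about 5% in the simulations.

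The cost is a SAP edit and one documented departure from the protocol; no new data are needed. If the sponsor prefers to keep the protocol's test as confirmatory, a prespecified supportive CMH stratified by baseline MMPS-P, alone or with MMPS, would show whether the result is robust to imbalance, but without the power gain.
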